8.6 Dosing Summary

The number of infusions and cumulative dose and duration of exposure to UX003 per subject in this study will be summarized. Treatment compliance will be displayed.

8.7 Efficacy Analyses

Because the primary objective of this study is to evaluate the long-term safety, the efficacy parameters will not be grouped into primary or secondary categories.

The percent change in uGAG excretion will be analyzed using the generalized estimating equation (GEE) method. Model will include baseline a covariate and visit (in this study) as a factor. The covariance structure within subjects will be assumed to be exchangeable.

Descriptive statistics will be presented by assessment time point for observed and change from baseline for the following other efficacy parameters.

- Biomarkers of inflammation in serum
- 6MWT and the percent predicted 6MWT value
- BOT-2
- 3MSCT
- Pulmonary function testing (eg., FVC, FEV and MVV1)
- Shoulder range of motion (goniometry) in extension and flexion by shoulder and the average of the right and left shoulders.
- Visual acuity
- Fatigue
- MPS HAQ
- CHAQ
- HAQ
- Scoring of impactful clinical problems
- Cardiac ventricular mass

Descriptive statistics will be presented by assessment time point for the following other efficacy parameters.

- MDRI
- Fatigue MID
- Subject/Parent/Caregiver CGI scales
- Hepatosplenomegaly

For growth, anthropometric measurements with z scores and percentiles will be summarized by historical time point and on study visit. For naïve subjects, the slopes of growth velocities will be summarized for pre (historical up to 2 years and baseline data) and post (baseline and post treatment data) treatment periods. For IST subjects, the growth velocities will be calculated for pre-initial UX003 treatment (up to 2 years) and post-initial UX003 treatment. For rollover subjects, the growth velocities will be calculated for pre first treatment in the feeder study (up to 2 years) and post first treatment in the feeder study.

For ICR, whether a positive change, according to the MID criteria, has occurred in the prespecified ICR will be assessed. The percentage of subjects achieving an ICR MID will be calculated for the rollover subjects and presented by assessment time point.

- 8.8 Safety Analyses
- 8.8.1 Adverse Events

The latest Medical Dictionary for Regulatory Activities (MedDRA) will be used to code all AEs to a system organ class (SOC) and preferred term.

An AE (classified by preferred term) will be considered a treatment emergent adverse event (TEAE) if it occurred on or after the first dose in this study, and was not present prior to the first dose in this study, or it was present at the first dose in this study but increased in severity during the study.

Subject incidence of TEAEs will be tabulated by SOC and preferred term. Serious adverse events (SAEs), treatment-related TEAEs and treatment-related SAEs will also be summarized.

Detailed listings for all AEs, SAEs, treatment related TEAEs, treatment related SAEs, AEs leading to the discontinuation, and death will also be generated. The severity will be based on Common Terminology Criteria for Adverse Events (CTCAE). If an AE cannot be graded based on CTCAE, the investigator will assign a severity based on 1 = mild, 2 = moderate, 3 = severe, 4 = life threatening, and 5 = Death related to AE.

Patterns of Infusion Associated Reactions (IARs) will be specifically evaluated throughout the study. IARs will be characterized into 4 distinct types based on timing of onset relative to the infusion and specific clinical manifestations: anaphylactoid, anaphylaxis, urticarial (with or without angioedema), and immune complex. Safety reporting of individual AEs will be recorded in parallel. Detailed listings of IARs will be provided.

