#### 7.6.5 Efficacy endpoints

The percentage change from pre-treatment baseline in uGAG and changes from pre-treatment baseline for other efficacy endpoints will be described across subjects in terms of the mean and standard deviation. The percentage change from pre-treatment baseline in uGAG will be tested using the GEE method. The GEE model will include baseline and time as categorical variables.

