3.6 Randomization and Blinding

All subjects received UX003 on an open-label basis. Randomization, blinding and stratification factors are not needed for this study design.

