8 STATISTICAL METHODS OF ANALYSIS

8.1 General Principles

All analysis will be performed based on full analysis set, and summaries will be presented overall and for naïve, IST and rollover subjects separately. The statistical analyses will be reported using summary tables, figures, and data listings. Statistical tests will be 2-sided at the alpha =0.05 significance level. All p-values will be presented as nominal p-values. Continuous variables will be summarized with means, standard deviations, medians, minimums, and maximums. Categorical variables will be summarized by counts and by percentages of subjects in corresponding categories. All raw data obtained from the CRFs as well as any derived data will be included in data listings.

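### The single-arm uGAG model conditions on baseline, so the usual standard error omits sampling error in the baseline mean and the 95% intervals are somewhat too narrow (minor)

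*SAP*

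**What the plan says.** The study has no comparator. SAP 3.6 states that "All subjects received UX003 on an open-label basis" and that "Randomization, blinding and stratification factors are not needed for this study design".

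SAP 8.7 sets the model: "The percent change in uGAG excretion will be analyzed using the generalized estimating equation (GEE) method". It continues "Model will include baseline a covariate and visit (in this study) as a factor" and "The covariance structure within subjects will be assumed to be exchangeable". Protocol 7.6.5 makes this a formal test: "The percentage change from pre-treatment baseline in uGAG will be tested using the GEE method". SAP 8.1 adds "Statistical tests will be 2-sided at the alpha =0.05 significance level", with p-values labelled nominal, and Protocol 7.6.3 adds two-sided 95% confidence intervals.

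Protocol 7.6.5 and the synopsis describe the model differently: "The GEE model will include baseline and time as categorical variables".

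For uGAG, SAP 5.1 averages the pre-dose assessments of naïve and IST subjects. Rollover subjects keep the feeder-study baseline, and the number of samples behind it is not given. Neither document names the baseline value at which the visit mean is evaluated, the type of standard error, or any allowance for error in the baseline mean.

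**The concern.** In a comparison of two arms, adjusting for baseline removes noise and the baseline mean cancels from the difference. Here the tested quantity is the mean change in one arm. Each subject's baseline measurement error enters that subject's change at every visit, so it is part of the uncertainty of the mean change. Regressing change on baseline moves some of that variation out of the residuals, and a standard error built from the residuals no longer counts it. The estimate still carries it.

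What is at stake is interval coverage. Protocol 5.2 and 7.5.3 tie clinical benefit to uGAG reductions above 50%, and Protocol 7.4.3 reports mean reductions of about 60% at the study dose. Readers will therefore look at the interval bound nearer 50%. With up to 20 subjects, and an analysis of 8 rollover subjects planned to support filing (SAP 3.4), interval width matters.

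**Working it through.** The documents contain no sample size calculation, power or uGAG variance, so there is no planned figure to reproduce. The benchmark is the nominal 5% miss rate of a 95% interval.

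**Inputs from the documents.** N up to 20 (SAP 3.3). uGAG every 12 weeks to Week 144 (Schedule of Events), so 144/12 = 12 post-baseline visits. Single arm, two-sided alpha 0.05, exchangeable working covariance.

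**Assumed inputs, not in the documents.** Between-subject log SD 0.45; within-subject log SD s = 0.2, 0.3 and 0.4; one, two or three baseline samples; between-subject SD of the response (log scale) 0 or 0.2.

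**Step 1, algebra.** Let D be a subject's mean change over visits, X the baseline and b the slope of D on X. For complete data the fitted mean at the average X equals the raw mean of D.

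- True variance of that mean: (residual variance + b² × Var(X)) / n.
- Variance reported by the model: residual variance / n.
- Ratio of reported to true SE: sqrt(1 − R²), where R² is the share of Var(D) explained by X.

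The ratio cannot exceed 1 apart from degrees-of-freedom scaling. A noisy baseline gives a negative slope even when nothing changes.

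**Step 2, mechanism check on the log scale** (not the planned scale). One baseline sample, no response variation, s = 0.3:

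- R² = 0.3⁴ / [(0.45² + 0.3²)(0.3² + 0.3²/12)] = 0.0081 / (0.2925 × 0.0975) = 0.284.
- SE ratio = sqrt(0.716) = 0.85.

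For a single visit, replace 0.3²/12 by 0.3²: R² = 0.0081 / (0.2925 × 0.18) = 0.154 and the ratio is 0.92. The loss is therefore smaller for one visit than for the average over visits. In three simulated log-scale data sets the GEE estimates were identical with and without the covariate. The sandwich SEs were 0.059, 0.053 and 0.059 with it, and 0.066, 0.072 and 0.077 without it.

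**Step 3, planned percent-change scale.** Simulation with n = 20, 12 visits, t reference and no true change. SE ratio is with covariate / without covariate, using average SEs, for s = 0.2 / 0.3 / 0.4:

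| Baseline samples, response SD | SE ratio | Miss rate with covariate | Miss rate without |
|---|---|---|---|
| 1, SD 0 | 0.93 / 0.88 / 0.84 | 6.9 / 8.8 / 10.4% | 5.3 / 5.8 / 6.0% |
| 2, SD 0.2 | 0.99 / 0.96 / 0.93 | 5.3 to 7.7% | 5.2 to 6.0% |
| 3, SD 0.2 | 1.00 / 0.98 / 0.96 | within about 5 to 8% | about 5 to 6% |

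Taking the median of the per-trial ratios gives 0.95 / 0.89 / 0.85 in the first row and about 0.94 to 1.0 in the other two. In round terms the SE is about 5-15% too small in the least favourable case and about 0-6% in the others. Miss rates are measured against the true mean percent change, so they isolate the variance defect.

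**Step 4, at a true 60% reduction** (one baseline sample, no response variation). The miss rate is 6.6 / 8.3 / 10.9% with the covariate and 5.2 / 5.2 / 6.6% without it. Zero is rejected in 99.5-100% of runs. The SE difference is 0.1 to 0.7 percentage points, so with a t multiplier of about 2.1 the bound moves by about 0.2 to 1.5 points. With two samples and response SD 0.2 the SE difference is at most 0.3 points, or about 0.6 at the bound.

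**Step 5, eight subjects at one visit** (between-subject log SD 0.3, within 0.2, one baseline sample, sandwich SE with normal reference). The miss rate is 16.9% with the covariate and 11.8% with the baseline term restored to the variance. The excess of 11.8% over 5% is small-sample sandwich bias, a separate matter. This applies only if the same model is used for that analysis; SAP 3.4 does not say.

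**The case against.** The strongest reply is that this changes no conclusion. At the anticipated effect, zero is excluded whichever standard error is used. The primary objective is safety, SAP 8.7 does not rank efficacy parameters, p-values are nominal, and Protocol 7.6.5 also reports the plain mean and SD, from which an unconditional interval can be formed. Averaging pre-dose samples under SAP 5.1 shrinks the defect, and so does true variation in response. The SAP also names no evaluation point: a prespecified fixed reference baseline would avoid the defect, though it would change what is estimated. All of this stands and limits the point to a minor one. It does not remove it. Nothing in the plan restores the missing variance, the rollover baseline may rest on a single sample, and calling p-values nominal does not correct an interval.

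Three stronger readings are tempting, and the documents do not support them.

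- A reader might infer that the model would often declare an effect where none exists, and cite high rejection rates for percent change under no change. Those rates mix in a different problem. Dividing by a noisy baseline makes the mean percent change positive when nothing has changed: exp(s²) − 1 gives about 4, 9 and 17 points for s = 0.2, 0.3 and 0.4. Dropping the covariate leaves that bias in place.
- A reader might take the protocol's wording to mean one baseline category per subject, which would make the standard error collapse. The protocol defers the full description to the SAP, and the SAP treats only visit as a factor. The mismatch needs correcting but does not describe the operative model.
- A reader might treat a model with baseline as the first repeated outcome as an equivalent remedy. It is not equivalent when the outcome is percent change.

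**Conclusion.** The concern holds as a minor point about interval coverage. With the visit mean evaluated at the observed average baseline, the SAP 8.7 model gives a standard error that omits sampling error in the baseline mean. Under the assumed SDs it is about 5-15% too small with a single baseline sample and no response variation, and the 95% interval misses about 7-11% of the time against about 6%. With two or three averaged samples and response SD 0.2 it is about 0-6% too small, and the miss rate is about 5-8% against 5-6%. The conclusion that uGAG falls is not in doubt at the anticipated reduction. What is affected is the precision claimed for the size of the fall, notably the bound relative to 50%. The direction follows from algebra. The size depends on variances and baseline sample counts that the documents do not give.

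**What to change.** In SAP 8.7, for the test and 95% confidence interval of percent change in uGAG, fit visit only, without the baseline covariate. Report the relation of response to baseline separately as a descriptive analysis. A model with baseline as the first repeated measure is an alternative only if the outcome is changed to absolute or log uGAG. Correct the model sentence in Protocol 7.6.5 and the synopsis, where baseline is listed as categorical, so that it matches the amended SAP model.

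This is a one-line model change and a wording correction, with no new data. The cost is slightly wider intervals. From the median SE ratios, the single-sample case widens by about 1/0.95 = 1.05 to 1/0.85 = 1.18 times, and the averaged-sample cases by at most about 1/0.94 = 1.06 times. With complete data the estimate itself does not change.

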#### 7.6.3 Statistical Principles

Continuous variables will be summarized by number of subjects and mean, standard deviation (SD), median, minimum, and maximum values. Categorical variables will be summarized by number and percentage of subjects. Statistical tests will use 2-sided alpha =0.05 significance level. Two-sided 95% confidence intervals will also be presented Safety and Efficacy analysis will all be based on Full Analysis Set using observed data. Missing values will not be imputed, unless otherwise specified.

The analyses planned in this protocol will be expanded in the UX003-CL202 SAP. The SAP will be approved prior to the database lock. Any deviations from the analyses described in the protocol and SAP will be noted in the final clinical study report (CSR).

The statistical analyses will be reported using summary tables, figures, and data listings. . All analyses and tabulations will be performed using  $SAS^{\circledast}$ . All raw data obtained from the CRFs as well as any derived data will be included in data listings.

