7.4 Software

SAS[®] software version 9.4 or higher will be used to perform most or all statistical analyses.

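### The uGAG GEE in about 20 subjects has no stated variance estimator, reference distribution or small-sample correction; if run with an uncorrected sandwich and normal quantiles, its 95% intervals would be about 11% too narrow

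*SAP*

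**What the plan says.** The secondary objective is long-term reduction of uGAG. Protocol 7.6.5 plans a test: "The percentage change from pre-treatment baseline in uGAG will be tested using the GEE method". It describes the model in one line: "The GEE model will include baseline and time as categorical variables". SAP 8.7 restates it as "Model will include baseline a covariate and visit (in this study) as a factor" and adds "The covariance structure within subjects will be assumed to be exchangeable".

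On inference, SAP 8.1 says "Statistical tests will be 2-sided at the alpha =0.05 significance level" and "All p-values will be presented as nominal p-values". Protocol 7.6.3 says "Two-sided 95% confidence intervals will also be presented" and bases the analysis on observed data without imputation unless otherwise specified. SAP 7.4 gives only the package: SAS "software version 9.4 or higher will be used to perform most or all statistical analyses".

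The sample is approximately 20 subjects (Protocol 7.6.1) or at most 20 (SAP 3.3), with no formal sample size calculation. uGAG is measured every 12 weeks to Week 144.

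Neither document states a variance estimator, a reference distribution or a small-sample method for this GEE, and neither rules one out.

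**The concern.** This GEE is the only efficacy model with a planned test. The number of independent units is the number of subjects, about 20; twelve visits each do not add to it. With so few units, the ordinary empirical (sandwich) variance is biased downward because it uses fitted residuals as if they were true errors. A normal quantile also ignores the uncertainty in that variance. Both effects make intervals too short.

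Because the SAP is silent, two programmers could follow it exactly and report different intervals. At stake is whether the 95% intervals around the uGAG estimates have the coverage the protocol promises. The degrees of freedom for any correction also depend on how baseline enters, and the two documents describe that differently: a covariate in SAP 8.7, a categorical variable in Protocol 7.6.5.

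**Working it through.** The documents state no coverage, power or variance figure to reproduce. The benchmark is the nominal 95%.

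**Inputs from the documents.** N = 20 (Protocol 7.6.1, SAP 3.3). Twelve post-baseline uGAG visits: Weeks 12, 24, 36 and 48, plus the eight from Week 60 to Week 144 (schedule of events, note d). Baseline term, visit factor, exchangeable working covariance (SAP 8.7). Two-sided 0.05 and 95%.

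**Assumed, because the documents give no values.** Within-subject correlation (exchangeable 0.6 or AR(1) 0.8), error shape (normal, or lognormal with log-scale SD 0.5, skewness 1.75) and missingness (none, or 30% monotone dropout at random).

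**Step 1: one visit, normal errors, continuous baseline, closed form.** The uncorrected sandwich variance of the mean at average baseline is (sum of squared residuals)/N². The unbiased version divides by N(N-2). The sandwich standard error is therefore too small by a factor sqrt((N-2)/N).

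- Multiplier actually applied: 1.96 × sqrt(18/20) = 1.859.
- Multiplier needed: t(18) = 2.101.
- Coverage: P(|t(18)| < 1.859) = 92.1%.
- Width ratio: 1.859/2.101 = 0.885, so the interval is 11.5% too narrow.

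**Step 2: twelve visits, simulation.** Coverage of the nominal 95% interval for a visit mean, averaged over visits. Ranges span both correlation structures, with and without dropout, from two independent runs of 10,000 and 8,000 replicates:

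| Method | Normal errors | Lognormal, skewness 1.75 |
|---|---|---|
| Uncorrected sandwich, z | 91.5-92.5% | 89.3-90.6% |
| Model-based, z | 93.4-94.2% | 92.7-93.9% |
| Kauermann-Carroll, t(N-2) | 94.4-95.1% | 92.3-93.2% |
| Mancl-DeRouen, t(N-2) | 95.3-96.0% | 93.3-94.1% |

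The simulated width ratio of sandwich-with-z to Kauermann-Carroll-with-t is 0.892-0.898. At 0.894, the uncorrected interval is about 11% too narrow and the corrected one 1/0.894 = 1.12 times as wide.

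**Step 3: cost of Mancl-DeRouen.** The uncorrected standard error is 0.894 × 2.101/1.96 = 0.958 of the Kauermann-Carroll one. Mancl-DeRouen applies roughly the same inflation a second time, 1/0.958 = 1.044. Its interval is therefore about 1.12 × 1.044 = 1.17 times the uncorrected width.

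**Step 4: sensitivity.** With stronger skew (3.7), sandwich-with-z covers 87.1-87.5% and Kauermann-Carroll with t covers 89.8-90.0%. If the SD rose linearly from 0.7 to 1.3 of its average across visits, model-based with z would cover 99.2-99.4% at the first visit and 84.0-87.0% at the last. Kauermann-Carroll with t would stay at 94.3-95.6% throughout. With a three-level categorical baseline, sandwich-with-z covers 91.9-92.0%, and Kauermann-Carroll with t on N-3 degrees of freedom covers 95.1-95.2%.

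**The case against.** The strongest reply is that little turns on this. The primary objective is safety, the design is single-arm and open-label, p-values are nominal, and SAP 8.7 declines to rank the efficacy parameters. With mean reductions of about 60% seen at this dose in the Phase 1/2 study (Protocol 7.4.3), a test against zero will almost certainly give the same answer under any variance estimator. This stands, and it limits the severity.

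The second reply is that nobody has said the uncorrected sandwich with z will be used. That also stands. A reader might infer that the trial will report 90-92% intervals; the documents do not support this, because they are silent. Model-based errors with z fall short by only about one to two points in these settings. Their poor last-visit coverage appears under a constructed variance trend that nothing in the documents suggests. Protocol 5.2 describes uGAG reaching a plateau after 4-6 weeks in other MPS programmes, which is before Week 12. That does not establish constant variance, but it means the trend is an illustration of dependence on an assumption and not a forecast.

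Two further inferences are tempting. One is that the analysis after the first 8 rollover subjects (SAP 3.4) makes the problem much worse. Neither that section nor the subgroup summaries in SAP 8.1 say that a GEE will be fitted to so few subjects, so this gives no support here. The other is that the limits will be judged against the 50% reduction that Protocol 7.5.3 calls clinically meaningful. Readers may look, but no formal comparison is planned.

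A last reply is that choosing one correction over another is preference. This is partly right: under skew, Kauermann-Carroll with t is no better than model-based with z, and Mancl-DeRouen covers slightly better. The supportable request is that one of them be fixed in advance.

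**Conclusion.** The omission is certain; its numerical effect is conditional. Under the uncorrected sandwich with normal quantiles, nominal 95% intervals for uGAG visit means cover about 92% with normal errors, and about 90% with lognormal errors of skewness 1.75. They are about 11% too narrow. Under model-based errors with normal quantiles, coverage is about 93-94% provided the variance is the same at every visit. The 92% for a single visit follows in closed form from N = 20 and normal errors. The 90% rests on an assumed skewness, and correlation and dropout are assumed throughout.

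The consequence is a modest understatement of uncertainty around the one secondary objective. It does not put the conclusion that uGAG falls at risk, and no planned decision depends on it. Severity is minor to moderate. It goes beyond missing detail because a conventional run that obeys the SAP would not deliver the stated confidence level, and a better method is available cheaply.

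**What to change.** In SAP 8.7, keep the mean model and the exchangeable working covariance, and add:

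- Standard errors use a bias-corrected sandwich variance, either Kauermann-Carroll or Mancl-DeRouen, with one named before the analysis. Mancl-DeRouen covers slightly better under skew and is slightly conservative with normal errors.
- Intervals and tests use a t reference with degrees of freedom equal to the number of subjects minus the number of between-subject parameters: N-2 with a continuous baseline, N minus the number of levels with a categorical one.
- The same rule applies to any GEE that is fitted.
- Baseline is stated as continuous or categorical, reconciling SAP 8.7 with Protocol 7.6.5.

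The cost is a few sentences in a SAP amendment before database lock and a programming option or short macro. At N = 20, intervals become about 12% wider with Kauermann-Carroll and, by the approximation above, about 17% wider with Mancl-DeRouen, relative to the uncorrected sandwich with z. If percent changes are strongly skewed, coverage improves but does not fully reach 95%.
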